ISRCTN	International Standard Randomised Controlled Trials Number
MA	Marketing Authorisation

MHRA	Medicines and Healthcare products Regulatory Agency
MS	Member State
NHS R&D	National Health Service Research & Development
NIMP	Non-Investigational Medicinal Product
PI	Principal Investigator
PIC	Participant Identification Centre
PIS	Participant Information Sheet
QA	Quality Assurance
QC	Quality Control
QP	Qualified Person
RCT	Randomised Control Trial
REC	Research Ethics Committee
SAE	Serious Adverse Event
SAM	Synthetic Absorption Matrix
SAR	Serious Adverse Reaction
SDV	Source Data Verification
SOP	Standard Operating Procedure
SmPC	Summary of Product Characteristics
SSI	Site Specific Information
SUSAR	Suspected Unexpected Serious Adverse Reaction
TMF	Trial Master File
TMG	Trial Management Group
TSC	Trial Steering Committee

iii. TRIAL SUMMARY

Trial Title	A pilot, randomised, double-blind, placebo-controlled, cross-over study of metformin to reduce airway glucose in chronic obstructive pulmonary disease (COPD)	
Internal ref. no. (or short title)	A pilot study of metformin to reduce airway glucose in COPD	
Clinical Phase	Exploratory Phase II pilot study	
Trial Design	Randomised, double-blind, placebo-controlled, cross-over	
Trial Participants	Chronic obstructive pulmonary disease (COPD) patients	
Planned Sample Size	40 subjects	
Treatment duration	3 months one study arm, 2 weeks wash out, 3 months in other study arm	
Follow up duration	6.5 months	
Planned Trial Period	24 months	
	Objectives	Outcome Measures
Primary	Effect of metformin on airway glucose	Sputum glucose after 3 months treatment with metformin
Secondary	Effects of metformin on: 1. Glucose levels in the nose 2. Bacterial infection 3. Inflammation in the lung 4. COPD exacerbations 5. Quality of life and symptoms 6. Lung function	1. Glucose levels in nasal SAM strips 2. Bacterial load in sputum 3. Inflammatory markers in sputum 4. Number of COPD exacerbations 5. Quality of life and symptom scores 6. Spirometry
Investigational Medicinal Product(s)	Metformin	
Formulation, Dose, Route of Administration	1000mg bd, po	

iv. FUNDING AND SUPPORT IN KIND

FUNDER(S) (Names and contact details of ALL organisations providing funding and/or support in kind for this trial)	FINANCIAL AND NON FINANCIAL SUPPORT GIVEN
NIHR Imperial Biomedical Research Centre (BRC)	£ 173,511

v. ROLE OF TRIAL SPONSOR AND FUNDER

[figure not shown]
Imperial College is the Trial Sponsor responsible for the initiation and management of the trial. The funder had no input into the trial design, conduct, data analysis and interpretation, manuscript writing, and dissemination of results

vi. ROLES AND RESPONSIBILITIES OF TRIAL MANAGEMENT COMMITTEES/GROUPS & INDIVIDUALS

vii. Protocol contributors

The protocol was written by [name], [name] and [name].

viii. KEY WORDS: COPD, lung glucose, metformin, pilot study, cross-over trial

1 BACKGROUND

Chronic obstructive pulmonary disease (COPD) is the 4th leading cause of death worldwide and continues to increase in prevalence (1). Lung infection plays a major role in disease progression and acute exacerbations. Bacterial infection is detected in 30-40% of stable COPD patients and is associated with disease progression, airway inflammation, impaired quality of life, more symptoms and frequent exacerbations (2). COPD patients frequently experience acute exacerbations that are associated with enormous morbidity, mortality and frequent hospitalisation, and bacteria are detected in 50-60% of exacerbations (2). Use of antibiotics to treat COPD exacerbations contributes to the development of antibiotic resistance. Therefore there is a clear unmet medical need to develop antibiotic-independent approaches to reduce bacterial infection in COPD. This has the potential to improve outcomes in COPD and reduce exacerbations. Glucose concentrations in the lungs are increased in COPD patients and linked to bacterial infection (3). This suggests that reducing airway glucose may be a promising potential therapeutic strategy

2 RATIONALE

COPD affects 1.2 million people in the UK, costing the NHS >£800 million annually. COPD patients are more susceptible to both chronic and acute bacterial infections. Patients with chronic lung bacterial infection have worse quality of life, faster disease progression, more symptoms and frequent exacerbations. Acute respiratory infections are the main cause of acute COPD exacerbations which cause COPD patients to become acutely unwell and often result in hospitalisation, especially in the winter. Bacteria are detected in 50-60% of COPD exacerbations. Antibiotics are frequently used to treat COPD exacerbations and this contributes to the development of antibiotic resistance. Therefore any intervention that prevents or reduces bacterial infection in COPD, especially if it is not an antibiotic, will have major benefits for COPD patients, the NHS and for society as a whole.

It is likely that there are many reasons why COPD patients are more susceptible to bacterial infections. From experimental work we have carried out we believe that one of the reasons is high glucose concentrations in the lung (3). In healthy lungs glucose levels are kept low and this is probably to inhibit bacterial growth by depriving them of an essential nutrient. In animal studies if levels of glucose in the lung are high, bacterial lung infection is more common (4). We measured lung glucose concentrations in COPD patients and found that they are higher compared with people without COPD.

COPD patients with higher levels of glucose also had more bacteria in their lungs and sputum samples from COPD patients with higher glucose concentrations supported greater bacterial growth (3).

Therefore this study was the first to link elevated glucose in the lung to bacterial infection in COPD. Therefore reducing airway glucose has the potential to inhibit bacterial growth in COPD patients. One potential approach is to use the anti-diabetic drug metformin. In animal studies we have demonstrated that metformin decreases airway glucose and bacterial colonisation (4). The aim of the proposed study is to investigate whether metformin can achieve the same effects in COPD patients. Metformin is safe, cheap, does not cause hypoglycaemia and has been extensively used in COPD patients with diabetes with an excellent safety record (5). The primary aim of this study will be to evaluate the effects of metformin on lung glucose in COPD patients. If the study successfully demonstrates that metformin reduces airway glucose it will provide the data needed to justify a clinical trial of metformin with exacerbations as the primary outcome.

2.1 Assessment and management of risk

Risks related to metformin

The side effects of metformin are mainly gastrointestinal. The relevant summary of product characteristics (SmPC) lists gastrointestinal disorders, such as nausea, vomiting, diarrhoea, abdominal pain and loss of appetite, as very common (frequency $>1/10$). It states that these side effects 'occur most frequently during initiation of therapy and resolve spontaneously in most cases.' Taste disturbance is listed as a common side effect (frequency $>1/100$). All other side effects are described as very rare ($<1/10,000$) or not known (cannot be estimated from available data). In accordance with the SmPC, to minimise gastrointestinal effects as far as possible, the study tablets will be administered after meals, and the dose will be escalated gradually to the target dose.

Hypoglycaemia:

Metformin does not induce low blood sugar levels (hypoglycaemia) when used as the sole glucose-lowering therapy in diabetic patients. It does not exert a hypoglycaemic action in non-diabetic patients unless taken in overdose. Even in the setting of overdose, hypoglycaemia has not been seen with metformin doses up to 85g. As diabetes is an exclusion criterion, the use of other oral glucose-lowering agents will not be permitted in this study.

Although not listed in the SmPC, it is suggested that there may be a risk of hypoglycaemia if metformin is administered in the setting of malnutrition, inadequate caloric intake, or excessive alcohol consumption. Therefore these will be exclusion criteria in this study.

Lactic acidosis:

A predecessor of metformin - phenformin - has been associated with lactic acidosis. However a systematic review published in 2010 evaluated the risk for lactic acidosis in type 2 diabetic patients taking metformin and showed no cases of fatal or nonfatal lactic acidosis in 347 prospective trials and cohort studies with more than 70,490 patient-years of metformin use. The authors concluded that there is no evidence that metformin is associated with an increased risk of lactic acidosis (6).

Metformin and COPD

Metformin is routinely used in COPD patients who also have diabetes. There are 3 studies of metformin use in COPD patients and serious adverse effects were not reported. In fact these studies found that COPD patients taking metformin had less breathlessness, less exacerbations, less hospitalisations and longer survival (5, 7, 8). A systematic review and meta-analysis of the adverse effects of metformin in polycystic ovarian disease (PCOS) also found that metformin was safe and well-tolerated (9). Therefore from the available studies metformin has been reported safe in COPD (and may actually have beneficial effects) and in non-diabetic patients with PCOS.

Risks related to study procedures

Sputum induction carries a small risk of bronchoconstriction. We have performed sputum inductions in COPD patients for >15 years and we have a well-established protocol to minimise the risk of bronchoconstriction and detect immediately if it occurs. Using this protocol we have carried out >350 inductions with no adverse events, including in patients with severe COPD and in COPD patients during acute exacerbations

This trial is categorised as:

- Type B (somewhat higher than the risk of standard medical care). As the study participants will be taking additional medication to their usual medical care there is an increased risk of adverse effects. However as the medication is licensed and has been extensively used in this population group with minimal adverse effects (and possibly beneficial effects – see references 5, 7 and 8) this study is not Type C (Markedly higher the risk of standard medical care).

3 OBJECTIVES AND OUTCOME MEASURES/ENDPOINTS

3.1 Primary objective

To determine the effect of metformin on the glucose in sputum in COPD patients after 3 months treatment with metformin.

3.2 Secondary objectives

Secondary objectives will be to determine the effect of metformin on:

- 1) Nasal glucose
- 2) Bacterial infection
- 3) Inflammatory markers in sputum
- 4) COPD exacerbations
- 5) Quality of life and symptoms
- 6) Lung function

3.3 Outcome measures/endpoints

3.4 Primary endpoint/outcome

The median concentration of glucose in sputum in COPD patients after 3 months treatment with metformin compared with 3 months of placebo.

3.5 Secondary endpoints/outcomes

These will also be assessed in COPD patients after 3 months treatment with metformin compared with placebo.

- 1) Median glucose concentration measured in nasal SAM strips
- 2) Bacterial infection (sputum semi-quantitative culture)
- 3) Inflammatory markers measured in sputum
- 4) Number of COPD exacerbations
- 5) Quality of life/symptom scores
- 6) Lung function measured using spirometry

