6.1 Inclusion criteria

Age 40-85 years

A clinical diagnosis of COPD confirmed with spirometry (Post-bronchodilator FEV₁/FVC <70%)

A smoking history of at least 15 pack years

Absence of infection for at least 8 weeks prior to study entry

No use of antibiotics and oral corticosteroids at least 8 weeks prior to study entry

Able to understand and consent to the study procedures

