10.3.2 Primary outcome analysis

The primary endpoint (median sputum glucose in treated versus non-treated participants) will be analysed using a Mann-Whitney test. The post-treatment sputum glucose will also be compared with baseline glucose using Wilcoxon matched-pairs test. Similar methods will be used to analyse the secondary endpoints.

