10.3.3 Secondary outcome analysis

Same as for primary outcome

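### The bacterial endpoint of this cross-over trial inherits an unpaired between-treatment test, with no grading scale stated; a within-person comparison of positivity and grade should replace it

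*Combined protocol and SAP*

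**What the plan says.** The design (Sections 4 and 7) is a two-period cross-over: three months on one treatment, a two-week washout, then three months on the other.

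The bacterial outcome appears under two labels. The trial summary gives the measure as "Bacterial load in sputum". Section 3.5 gives "Bacterial infection (sputum semi-quantitative culture"), and the table in Section 3.7 repeats this. Neither place states a grading scale, a threshold for a positive culture or a value for no growth.

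Section 10.3.2 says: "The primary endpoint (median sputum glucose in treated versus non-treated participants) will be analysed using a Mann-Whitney test". It adds: "The post-treatment sputum glucose will also be compared with baseline glucose using Wilcoxon matched-pairs test". For the other outcomes it says only "Similar methods will be used to analyse the secondary endpoints", and Section 10.3.3 says "Same as for primary outcome". Nothing is specific to the culture result.

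On how common positive cultures may be, Section 1 says: "Bacterial infection is detected in 30-40% of stable COPD patients". Appendix 2 schedules sputum at the baseline of each period and at every monthly visit.

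**The concern.** Two features work against this endpoint. First, the only metformin-against-placebo comparison it inherits treats the two sets of results as if they came from different people. The matched-pairs test compares each treatment with baseline, so it is not a test against placebo. Second, an ordered culture grade has a floor. If most patients grow nothing, most values are tied there and a median summary says little.

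Reducing bacterial infection without antibiotics is the rationale in Sections 1 and 2, and this endpoint connects lower airway glucose to that benefit. Section 4 says the pilot should supply effect sizes for later trials. A non-significant result from a test that ignores the pairing could be misread as evidence that metformin has no antibacterial effect. The plan also names no paired positivity, clearance or new-growth estimate to carry forward.

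**Working it through.** **The plan's own figure.** There is none for this endpoint. The 30 subjects in Section 10.1 are for sputum glucose; 30 and 40 are used below only as numbers of completers and of recruits.

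**Inputs from the documents.** Culture-positive share p = 0.30 to 0.40 (Section 1); n = 30 or 40 (Section 10.1); unpaired rank test between treatments (Sections 10.3.2 and 10.3.3).

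**Assumptions, not in the documents.** Undetected means no growth. The background share applies to month-3 cultures under placebo. Positive cultures spread evenly over four grades. Correlation within patient is 0.6 on an underlying normal scale. Metformin halves the positive share.

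**1. Patients above the floor at entry.** 40 × 0.30 to 0.40 = 12 to 16; 30 × 0.30 to 0.40 = 9 to 12. Only these can show a reduction from their own baseline. The others can still differ between treatments at month 3 if they acquire growth under one and not the other.

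**2. Chance that one condition's median is no growth.** For even n, both middle values are at the floor when at most n/2 − 1 patients are positive, so the chance is P(Binomial(n, p) ≤ n/2 − 1).

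| n | p = 0.30 | 0.35 | 0.40 | 0.50 |
|---|---|---|---|---|
| 30 (≤ 14 positive) | 98% | 93% | 82% | 43% |
| 40 (≤ 19 positive) | 99% | 96% | 87% | 44% |

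Treating the conditions as independent, with no drug effect and p = 0.40, both medians are no growth with probability 0.825² = 68% at n = 30 and 0.870² = 76% at n = 40. If metformin halves positivity these rise to 82% and 87%. A larger benefit therefore makes a pair of medians less informative.

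**3. Why pairing matters.** For a difference between two results from the same person with common variance σ² and correlation ρ, the variance of the mean difference is 2σ²(1 − ρ)/n. An unpaired analysis uses 2σ²/n. With ρ > 0 it overstates the error, so its true false-positive rate falls below 5% and power is lost.

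**4. Simulated power for a halving of positivity** (two-sided 5%, correlation 0.6, 4,000 runs per row):

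| n | p on placebo | Unpaired Mann-Whitney | Paired Wilcoxon, metformin against placebo |
|---|---|---|---|
| 30 | 0.30 | 23% | 35% |
| 30 | 0.35 | 28% | 41% |
| 30 | 0.40 | 33% | 49% |
| 40 | 0.30 | 30% | 43% |
| 40 | 0.35 | 39% | 53% |
| 40 | 0.40 | 48% | 62% |

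A separate simulation under the same stated assumptions put the top of the unpaired range at 45%; nothing turns on that difference. With no drug effect, the unpaired test rejected in about 1% of runs and the paired test in about 4-5%. If positivity falls to a quarter, the unpaired test has about 64-94% power; near complete clearance it has at least 98%.

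**5. Positivity alone, unpaired.** Power for a halving is 28-39% with 30 per condition and 36-50% with 40. For 80% power, n = [1.96√(2p̄(1 − p̄)) + 0.842√(p₁(1 − p₁) + p₂(1 − p₂))]² / (p₁ − p₂)². With 0.40 against 0.20: (1.270 + 0.533)² / 0.04, or 82 per condition. With 0.30 against 0.15 it is 121.

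**The case against.** The strongest reply is that the plan never says this endpoint will be summarised by a median. That word is attached to sputum and nasal glucose only. What carries over is a set of rank tests, and these respond to a change in the positive share despite ties. This stands. A reader might infer that the comparison must come out as no growth against no growth whatever metformin does. The documents do not support that: step 4 shows the inherited test would probably detect a large effect. The supportable problem is avoidable loss of power for a moderate one.

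A reader might also infer from the entry criterion, "Absence of infection for at least 8 weeks prior to study entry", that stable carriers are excluded, because Section 1 calls bacteria in stable patients infection. The documents do not support this either. Appendix 2 places the eligibility assessment at screening and the first sputum sample at baseline, so no sputum culture is scheduled when eligibility is decided. Section 2 also separates chronic bacterial infection from acute respiratory infection. No change to that criterion follows from this point.

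Two further replies stand in part. The two labels are mostly shorthand, since a semi-quantitative culture is a graded measure of load; the real gap is the missing scale and threshold. And the inherited matched-pairs test against baseline does use within-person reductions and new growth, but it does not compare metformin with placebo.

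Finally, 30-40% is a background figure and may not match culture results in this cohort. That is why the 50% column is shown.

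**Conclusion.** The point holds in this form: the inherited between-treatment test ignores the pairing that the cross-over provides, on an endpoint where ties at the floor are likely and no scale is defined. Under the stated assumptions the cost is roughly 12 to 16 percentage points of power for a halving of positivity, and a false-positive rate near 1% instead of 5%. The gain from pairing depends on the assumed correlation of 0.6 and would shrink as that correlation falls. The median figures (82-99%) matter only if medians are reported, and they weaken quickly if positivity is nearer half.

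This is one of six secondary endpoints in an exploratory pilot, so it does not threaten the primary result. It is still worth correcting, because the endpoint carries the clinical rationale and the better analysis needs no new data.

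**What to change.** - Use one definition in the trial summary and Sections 3.5 and 3.7: semi-quantitative sputum culture grade at month 3 of each period. State the grades, the threshold for positive and the value given to no growth.
- In Section 10.3.3, replace the inherited unpaired test for this endpoint with a within-person metformin-against-placebo comparison. Report the paired difference in the proportion culture-positive with its confidence interval (positive on metformin only minus positive on placebo only, divided by the number of pairs), and a paired analysis of the ordered grade.
- Report clearance or grade reduction among those positive, and new growth among those negative, descriptively and by culture status at the start of each period. Using the second-period baseline avoids counting a patient who cleared in the first period as clearing again in the second.
- State that a non-significant result will be read as an estimate with its interval and not as evidence of no effect.

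The cost is wording only, since Appendix 2 already schedules sputum at both baselines and at month 3 of both periods. There are downsides. Patients without a month-3 culture in both periods drop out of the paired comparison, the groups by culture status will be small, and power for a moderate effect stays low even with pairing.

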3.6 Exploratory endpoints/outcomes

Nil

3.7 Table of endpoints/outcomes

Objectives	Outcome Measures	Timepoint(s) of evaluation of this outcome measure (if applicable)
Primary Objective To determine the effect of metformin on sputum glucose in COPD patients	The median concentration of glucose in sputum in COPD patients after 3 months treatment with metformin compared with placebo.	3 months
Secondary Objectives To determine the effect of metformin on: 1) Nasal glucose 2) Bacterial infection 3) Inflammatory markers in sputum 4) COPD exacerbations 5) Quality of life and symptoms 6) Lung function	1) Median glucose concentration measured in nasal SAM strips 2) Bacterial infection (sputum semi-quantitative culture) 3) Inflammatory markers measured in sputum 4) Number of COPD exacerbations 5) Quality of life/symptom scores 6) Lung function measured using spirometry	3 months

4 TRIAL DESIGN

The proposed study will be a randomised, double-blinded, placebo-controlled, cross-over study of metformin in patients between the ages of 40 and 75 with a confirmed diagnosis of COPD. It will be an exploratory pilot trial, to gather preliminary information on the effects of metformin on sputum glucose and the feasibility of conducting a full-scale trial.

All subjects will have clinical assessments and blood, airway samples (nasal SAM and sputum) collected at baseline prior to the treatment phase. Clinical assessments will include lung function (FEV₁ and FVC), quality of life and symptom questionnaires (St George's Respiratory Questionnaire, COPD assessment test). Subjects will then either be commenced on metformin or placebo for a period of 3 months and blood, sputum and nasal samples collected at monthly intervals. Following a 2 week washout period the subjects will crossover to the other study arm for another 3 months and repeat samples collected.

Primary Outcome

The primary outcome will be sputum glucose measured using an enzymatic assay (AmplexRed® – ThermoFisher) after 3 months treatment with metformin. There is currently no data on which to base a power calculation and therefore this pilot study will assess what the size of any effect of metformin is in COPD subjects and thereby provide data that can be used to power any future, larger clinical trials.

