10.7 Participant population

The participant populations whose data will be subjected to the trial analysis will be the protocol-compliant population: Any participant who was randomised and received the protocol required trial drug exposure and required protocol processing

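### Section 4 promises an effect size to power later trials, but section 10.3.2 plans only tests, with no within-person estimate, confidence interval or variability; feasibility, the other stated aim, has no outcome

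*Combined protocol and SAP*

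**What the plan says.** Section 4 gives the pilot two purposes. It is "to gather preliminary information on the effects of metformin on sputum glucose and the feasibility of conducting a full-scale trial". On the first of these it adds that "this pilot study will assess what the size of any effect of metformin is in COPD subjects", so that later and larger trials can be powered from the result.

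The primary endpoint in section 3.4 is "The median concentration of glucose in sputum in COPD patients after 3 months treatment with metformin compared with 3 months of placebo". Sections 3.1 to 3.5 list one primary and six secondary objectives, all of them treatment effects. Section 3.6, "Exploratory endpoints/outcomes", is empty.

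Under section 10.3.2 the primary endpoint "will be analysed using a Mann-Whitney test". Post-treatment glucose is also "compared with baseline glucose using Wilcoxon matched-pairs test". Section 10.3.3 applies the same approach to the secondary outcomes.

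Section 10.7 states that the population for the trial analysis "will be the protocol-compliant population", meaning randomised participants with the required drug exposure and processing. Section 10.3.1 promises a CONSORT flow diagram, section 10.2 sets a recruitment target, and section 8.11 provides for diary cards and monthly counts of returned medication.

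**The concern.** A pilot meant to inform the design of another trial has to report how large the effect is, how uncertain that estimate is, and how much a person's value varies between periods. The last of these is what a cross-over is well placed to supply. The analysis named in section 10.3.2 asks for none of the three.

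If the plan is followed as written, the primary result is a pair of medians and p-values. A difference between two medians can be read off, but it has no interval and no paired variance, so it is a weak basis for sizing anything.

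The feasibility aim has a similar but smaller gap. It is stated once, in section 4, and no objective, outcome or analysis follows from it. The only population named for the trial analysis excludes people who did not receive the required exposure, and they are the people a feasibility question is largely about.

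**Working it through.** **1. Aim against analysis.**

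- *Effect size.* The outcome exists (section 3.4). The Mann-Whitney test treats the metformin and placebo values as independent samples, although each participant contributes to both. The Wilcoxon test is paired, but it compares post-treatment glucose with baseline, not metformin with placebo. So the within-person treatment difference is not formed in either analysis, and its SD does not emerge as a by-product.
- *Feasibility.* No entry appears in sections 3.1 to 3.6 or in 10.3. Raw material does exist: the recruitment target (10.2), diary cards and counts (8.11) and the flow diagram (10.3.1).

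**2. The plan's own sample size.** Inputs from section 10.1: median 1,007 µM, SD 733 µM, 30% reduction, 90% power, 5% significance (taken as two-sided), 30 subjects, 40 recruited.

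- Effect: 0.30 × 1,007 = 302.1 µM.
- Paired formula: n = (1.96 + 1.2816)² × SDd² / 302.1², where SDd is the SD of the within-person differences.
- With SDd = 733, n = 62 (64 with the t distribution). This does not reproduce 30.
- For n = 30 with a paired t test, SDd must be about 493 µM. With SDd = 733 × √(2(1 − ρ)), this means ρ = 1 − 493.3² / (2 × 733²) = 0.77. The protocol gives no correlation.
- The step to 40 does reproduce: 30 / (1 − 0.25) = 40.

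Whether 30 is justified is a separate matter. It is shown here because the answer turns on the same unreported quantity, ρ.

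**3. How much ρ matters for a later glucose cross-over.** The correlations are assumptions, since the documents give none. Raw scale, same effect and SD, 90% power, two-sided 5%, normal formula:

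| Assumed ρ | SDd (µM) | n |
|---|---|---|
| 0.3 | 867 | 87 |
| 0.5 | 733 | 62 |
| 0.8 | 464 | 25 |

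The range is 87 / 25 = 3.5-fold. On the ratio scale, treat 733 / 1,007 as a coefficient of variation (a further assumption, because 1,007 is a median). The log SD is then √ln(1 + 0.728²) = 0.652 and the effect is −ln 0.70 = 0.357. The same formula gives n = 50, 36 or 22 for ρ = 0.3, 0.5 or 0.7. The numbers are smaller, but they still depend on ρ.

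**4. What an interval would show.** With 30 pairs, the 95% CI half-width for the mean paired difference is t(0.975, 29) × SDd / √30. This is about 387, 274 or 212 µM for ρ = 0, 0.5 or 0.7, against a hoped-for effect of 302 µM. A p-value alone would not convey this imprecision.

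**5. Feasibility, for scale.** If 10 of 40 withdraw, as section 10.1 allows for, completion among all randomised is 30/40 = 75% (Wilson 95% CI 60% to 86%). The denominator has to be all 40 for this figure to be seen.

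**The case against.** The strongest reply is that the effect-size aim does have an outcome: medians on metformin and on placebo will be compared, and their difference is an effect size. This stands. A reader might infer that nothing in the protocol's outcomes serves either stated purpose, but section 3.4 rules that out for effect size. The gap lies in the analysis, where a bare difference in medians carries neither a CI nor a within-person variance.

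A reader might also infer that the compliant-only population would make retention and adherence look complete by definition. The documents do not support this. No section plans to calculate either figure in that population. The flow diagram would show losses among all randomised, section 8.11 counts medication for every participant, and section 9.2 records all adverse events. Section 10.7 gives no exposure threshold, and section 8.11 as written accepts noncompliance below 80%, so adherence among compliers need not be high.

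Third, the only follow-on trial the protocol describes (section 2) has exacerbations as its primary outcome, and a glucose correlation would not size it. This also stands. The figures in step 3 of the working bear only on a glucose cross-over, which section 4's general reference to future trials leaves open.

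Finally, feasibility is a single clause in section 4, and its lack of an outcome is mostly missing detail. This is fair, and it is why that part is secondary here.

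**Conclusion.** The point holds for the analysis. Section 4 promises an effect size fit for powering later trials, and section 10.3.2 does not produce one: it specifies no within-person metformin-placebo estimate, no confidence interval and no within-person variability. This conclusion comes from reading the sections together and needs no assumed figure.

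The size is illustrative only. The required number for a glucose cross-over ranges from 25 to 87 over assumed correlations of 0.8 to 0.3, using section 10.1's raw-scale inputs. It should not be read as a statement about the exacerbation trial.

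The feasibility part holds in a limited form. It is a stated aim without a defined outcome, and the one population named for the trial analysis would be the wrong denominator for it. Sections 8.11 and 10.7 do not agree on, or define, the required exposure and must be reconciled.

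The conflict between section 4's "There is currently no data on which to base a power calculation" and the power calculation in section 10.1 is a separate matter. This point does not depend on it.

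**What to change.** **Main change, section 10.3.2.** Make the main output the within-person metformin/placebo ratio of month-3 sputum glucose with its 95% CI. It can be obtained by taking each participant's difference in log glucose between the two periods and back-transforming the mean. Report the within-person SD, or the correlation between periods, on the same log scale, and say that it is intended for sizing later trials.

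**Secondary change, sections 3 and 10.7.** Add feasibility outcomes among all randomised participants, each with a 95% CI:

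- the proportion completing both periods;
- adherence in each period;
- the proportion with usable sputum glucose at both month-3 visits.

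State in section 10.7 that the protocol-compliant population does not apply to these. Reconcile sections 8.11 and 10.7 on what exposure is required. If feasibility is not really an aim, deleting the clause in section 4 would settle this secondary part, but not the main one.

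**Cost.** Protocol wording, slightly more analysis work and a few tables from assay results, diary cards, medication counts and participant flow that are already planned. No extra visit, sample or participant is needed. The feasibility figures may look less favourable than they would among compliers.
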